5.2.3 Assessments

CAN

A. Heart rate variability (HRV) studies: low and high frequency power (LF,HF), and time domain measures of HRV, standard deviation of normal RR interval(SDNN), root mean square of successive RR intervals (RMSSD) are analyzed from continuous ECG recordings using the ANX 3.1 software (ANSAR Inc., Philadelphia , PA) as described [35, 36].

B. Cardiovascular reflex tests will include: 1) changes in R-R interval with deep breathing, a measure of sinus arrhythmia during quiet respiration reflecting primarily parasympathetic function; 2) the R-R response to standing, inducing reflex tachycardia followed by

bradycardia which is jointly vagal and baroreflex-mediated; 3) the Valsalva ratio which evaluates cardiovagal function in response to a standardized increase in intrathoracic pressure (Valsalva Maneuver); and 4) orthostatic changes in BP. These tests are reproducible and considered as gold-standard [36, 37].

C. Resting heart rate

Subjects will be asked to avoid food, caffeine and tobacco products for at least 8 hours prior to testing, and hold any medication until testing was completed. Subjects who experienced a hypoglycemic episode after midnight [blood glucose \leq 50mg/dl (2.77mmol/l)] prior to the testing were rescheduled.

Cardiac function

We will measure serum BNP, by Chemiluminescent Immunoassay (CLIA) (Siemens, Erlangen, Germany) and will evaluate changes in BNP, as a biomarker for LV function. The blood draw will be performed at baseline and end of each study drug period.

Assessment of glucose variability

We will use a 14-day continuous glucose monitoring (CGM) using Abbott's Freestyle Libre Pro to evaluate and compare the indices of glucose variability [mean glucose, standard deviation (SD), coefficient of variation (CV), the mean amplitude of glycemic excursions (MAGE), low blood glucose index (LBGI) and area under the curve (AUC) for hypoglycemia] during each dapagliflozin and glimepiride intervention phase in patients with type 2 diabetes and also assess the association between the indices of glucose variability and changes in measures of HRV during each intervention period.

5.3 Procedures for handling subjects incorrectly enrolled or randomized or initiated on investigational product

The data management plan for this project is based on the randomization of 45 participants, with randomization occurring at the time of Visit 2. All candidates who complete the informed consent process will be assigned a study identification number (ID) at the time of Visit 1. Unless otherwise stipulated by the sponsor-investigator, the ID numbers are patient-specific and will be retained and associated with candidates who fail screening or are found to be ineligible, and/or drop-out prior to randomization. Follow-up will not be continued for candidates who do not proceed to randomization. Follow-up and research activities will be pursued on all randomized participants, even those candidates who may for some reason stop research medications.

5.4 Blinding and procedures for unblinding the study

5.4.1 Methods for ensuring blinding

The investigators will be blinded to the study drugs. The research pharmacy and participants will know the study drugs that participants will be on. The research pharmacy will be dispensing the study medications per the randomization schedule that will be provided by the study biostatistician.

5.4.2 Methods for unblinding the study

In the event of an emergency and a need to know study medications, the investigator will contact the Research Pharmacist and request identification of subject's test article assignment. The Research Pharmacist will indicate that the blind was broken on the Pharmacy Randomization Log and will document the date of the request, the name of the research personnel making the request, and the pharmacist's signature. The research coordinator will report the emergent event on the Adverse Event CRF and the unmasking event on the Unmasking Report CRF and then signed by the investigator.

5.5 Treatments

5.5.1 Identity of investigational product(s)

Dapagliflozin 5 mg tablet

Dapagliflozin is a sodium glucose transporter-2 (SGLT-2) inhibitor, a new class of glucose lowering agent that reduces hyperglycemia in patients with T2D by reducing renal glucose reabsorption.

Investigational product	Dosage form and strength	Manufacturer
Dapagliflozin	5 mg tablet	AstraZeneca
Glimepiride	1 mg tablet	Sanofi Aventis

5.5.2 Doses and treatment regimens

Participants will receive either open-label dapagliflozin 5 mg or open-label glimepiride 2 mg daily initially for 4 weeks then titrating the dose based on blood glucose levels up to dapagliflozin 10 mg daily or glimepiride 4 mg (no more than 4 mg daily) daily for 8 more weeks (total 12 weeks) followed by a 2-week washout period and then participants will receive the study drugs in reverse order to the first period for another 12 weeks.

5.5.3 Additional study drug

Glimepiride 2 mg tablet

Glimepiride is a sulfonylurea agent that reduces hyperglycemia in patients with T2D by stimulating insulin release from the pancreatic beta cells and reduction of glucose output from the liver.

5.5.4 Labeling

The label will include the following information: trial number, medication number.

Each medication box will contain an appropriate amount of dapagliflozin or glimepiride tablets, plus some reserve, for dosing until the next scheduled visit. Study drug will be supplied on a per Visit basis. Supply will be managed by University of Michigan Health System (UMHS) research pharmacy.

5.5.5 Storage

Dapagliflozin film-coated tablets and glimepiride tablets should be stored at 15° to 25°C (59° to 77°F) in a tightly closed container. The minimum/ maximum storage temperature must be measured and documented at least weekly by investigational drug store manager or pharmacist. All study medications will be contained in medication boxes identified with the trial number and medication number.

5.6 Concomitant and post-study treatment(s)

The research staff will record all concomitant drugs used by the subject in the source documents. This is to include prescription, non-prescription, homeopathic medications and dietary/vitamin supplements. At the screening visit, medication use is to be carefully reviewed to ensure that no contraindicated medications as described in the protocol are being used (e.g., beta blocker agents, phentermine). At all subsequent visits, subjects will be asked to report any changes to their reported medication use and the source document updated accordingly. Queries regarding medication exclusions and contraindications are directed to the study principle investigator.

5.7 Treatment compliance

Study staff will contact the subject within one week of initiating study medications to assess medication compliance and tolerance. All patients will be asked to bring their study medications with them to each study visit. The study staff will assess medication compliance and tolerance at each visit. Patients will be reminded about purpose of the study and importance of compliance with the study medications at each visit. Adverse events will be similarly recorded and reported as required. The study staff will also collect any unused study medication at the end of each intervention period. The number of unused dapagliflozin or glimepiride tablets will be recorded in the source document and unused medication secured until returned for final drug disposition.

5.7.1 Accountability

The pharmacist / investigational drug storage manager must maintain records of the trial medication's delivery to the trial site, the inventory at the site, the use by each patient, and destruction of unused medication. Proof of destruction will be provided to AstraZeneca at the end of the study. These records will include dates, quantities, batch/serial numbers, expiry ('use by') dates, and the unique code numbers assigned to the investigational product and trial patients. The pharmacist / investigational drug storage manager will maintain records that document adequately that the patients were provided the doses specified by the study protocol and reconcile all investigational products.

5.8 Discontinuation of investigational product

The study drugs will be discontinued in the following conditions:

1. Study patient withdraws consent.
2. Study patient fails to comply with the study protocol.
3. Study subject becomes pregnant.
4. If the study patient will need to be on concomitant drugs that may interfere with the study findings or study medications that may lead to higher risk of hypoglycemia, the study medication can be discontinued.
5. If the study patient develops persistent or recurrent serious side effects as described above (Section 1.4, 6.4.2 and 6.4.4), study drugs will be discontinued permanently.

5.8.1 Procedures for discontinuation of a subject from investigational product

If the study patient withdraws consent or who fails to comply with the study protocol or becomes pregnant, participation in the study will end and the study medication will be stopped. No further evaluation will be performed and no attempts should be made to collect additional data.

If a patient develops UTI or genital infection, we will manage the infection according to standard of care. However, a patient with persistent or recurrent UTI or genital infection despite standard of care, study medications will be hold temporarily until infections resolve. If a patient develops persistent serious adverse effects from study drugs (section 6.4.2 and 6.4.4), study medications will be discontinued permanently. And patients will be followed up until their serious adverse effects are completely resolved.

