5.9 Withdrawal from study

A subject may withdraw from the trial at any time at their own request, or they may be withdrawn at any time at the discretion of the investigator for safety, behavioral, or

administrative reasons. If a subject does not return for a scheduled visit, every effort should be made to contact the subject. In any circumstance, every effort should be made to document subject outcome, if possible.

If the subject withdraws consent, no further evaluations should be performed and no attempts should be made to collect additional data; however, they may be questioned regarding their reason for withdrawal and asked to return all unused investigational products.

Patients who withdraw or discontinue from the trial after randomization will not be replaced.

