6.4.2 Definitions of serious adverse event

A serious adverse event is an AE occurring during any study phase (i.e., treatment, washout, follow-up), that fulfils one or more of the following criteria:

- Results in death
- Is immediately life-threatening
- Requires in-patient hospitalization or prolongation of existing hospitalization
- Results in persistent or significant disability/incapacity or substantial disruption of the ability to conduct normal life functions
- Is a congenital abnormality or birth defect
- Is an important medical event that may jeopardize the subject or may require medical intervention to prevent one of the outcomes listed above.

The causality of SAEs (their relationship to all study treatment/procedures) will be assessed by the investigator(s) and communicated to AstraZeneca.

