13.2 Pregnancy

All female reproductive aged participants will be asked to use a definitive form of contraception before enrolling in the study. However, pregnancy might occur in the study period. Once a female subject has been enrolled into the clinical trial, after having taken study medication, the investigator must report immediately any drug exposure during pregnancy and stop the study medication. The outcome of the pregnancy associated with the drug exposure during pregnancy must be followed up. All outcomes of pregnancy should be reported to AstraZeneca.

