13.2.1 Maternal exposure

Dapagliflozin is pregnancy category drug C. Based on the results of reproductive and developmental toxicity studies in animals, dapagliflozin doses > 137 MRHD may affect renal development and skeletal malformation and maturation.

Glimepiride is pregnancy category drug C. There are no adequate and well-controlled studies in pregnant women. In animal studies there was no increase in congenital anomalies, but an increase in fetal deaths occurred in rats and rabbits at glimepiride doses 50 times (rats) and 0.1 times (rabbits) the maximum recommended human dose (based on body surface area).

As soon as we learn that a female subject has been pregnant, we will stop the study medication immediately. We will report this to AstraZeneca and IRBMED immediately. Patient will be asked to follow with her Obstetrician closely. We will also follow the pregnancy outcomes and report this to AstraZeneca.

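### Section 5.8.1 bars further data collection once a participant becomes pregnant, while Sections 13.2 and 13.2.1 require the pregnancy outcome to be followed and reported

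*Combined protocol and SAP*

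**What the plan says.** Section 5.8.1, on discontinuing a subject from study drug, opens with three triggers: withdrawal of consent, failure to comply, and pregnancy. For a patient who "becomes pregnant, participation in the study will end and the study medication will be stopped". The next sentence covers all three triggers: "No further evaluation will be performed and no attempts should be made to collect additional data".

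Section 13.2, on pregnancy, calls for immediate reporting of drug exposure and stopping of study drug, and continues: "The outcome of the pregnancy associated with the drug exposure during pregnancy must be followed up". It adds: "All outcomes of pregnancy should be reported to AstraZeneca". Section 13.2.1, on maternal exposure, says the same in the study team's voice: "We will also follow the pregnancy outcomes and report this to AstraZeneca".

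Three other places bear on the point:

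- Section 6.4.2 includes in its criteria for a serious adverse event (SAE): "Is a congenital abnormality or birth defect". The SAE form in the appendix has a matching question.
- Section 5.3 states: "Follow-up and research activities will be pursued on all randomized participants, even those candidates who may for some reason stop research medications".
- Section 5.9 uses almost the same no-data wording as 5.8.1, but attaches it only to consent: "If the subject withdraws consent, no further evaluations should be performed and no attempts should be made to collect additional data".

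**The concern.** Section 5.8.1 is where site staff would look when a participant has to stop study drug, and for pregnancy it tells them to stop collecting data. The duty to learn and report the outcome comes much later, in Section 13, and neither section points to the other.

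Staff who relied on 5.8.1 alone would not seek the outcome of a pregnancy exposed to study drug. That would leave a gap in fetal-safety information that the plan itself requires, and it could leave an event meeting the plan's own SAE definition undetected and so unreported within the 24 hours set in Section 6.4.3.

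**Working it through.** No figure in the plan depends on this point and there is nothing to calculate. The check is a comparison of the texts.

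| Question | Section 5.8.1 | Sections 13.2 and 13.2.1 |
|---|---|---|
| Does it cover pregnancy? | Yes, named as a trigger | Yes, the subject of the section |
| Study drug | Stopped | Stopped |
| Data after the pregnancy is known | None to be sought | Outcome to be followed |
| Reporting of the outcome | Not mentioned | To the manufacturer |
| Exception or cross-reference | None | None to 5.8.1 |

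1. **Same participant.** A woman who becomes pregnant after taking study drug falls under both rules. They agree on stopping drug and differ on what follows.
2. **Does following the outcome need new data?** Yes. The outcome lies in the future when the pregnancy is discovered. It can be learned only by contacting the participant or obtaining records later, and 5.8.1 rules out attempts to do that.
3. **Could 5.8.1 mean scheduled trial assessments only?** The wording has no such limit: it excludes any further evaluation and any attempt at additional data. The second paragraph of 5.8.1 does provide for follow-up to resolution after serious adverse effects of study drug. So the section states safety follow-up where it intends it, and gives none for pregnancy.
4. **Do the neighbouring sections agree with 5.8.1?** No. Section 5.9 ties the data stop to withdrawal of consent alone. Section 5.3 continues follow-up for every randomized participant who stops medication. Section 5.8.1 is therefore at odds with 5.3 as well, for pregnancy and for non-compliance.
5. **Does the SAE definition depend on the missing data?** Yes. A congenital abnormality or birth defect can be entered on the SAE form only if the outcome becomes known.

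**The case against.** The best defence is that 5.8.1 concerns the end of trial participation, so its data stop naturally means the scheduled assessments (heart rate variability, reflex tests, BNP, glucose monitoring). Pregnancy has its own section under a heading for procedures the investigator must follow. A reader who lets a specific rule override a general one would follow 13.2. The duty is stated there and again in 13.2.1, and the SAE form provides a place to record a birth defect. Section 5.9 also asks that subject outcome be documented where possible in any circumstance. On this view pregnancy was swept into a consent-withdrawal sentence by loose drafting, and nobody meant to forgo the outcomes.

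The defence adds that the event is unlikely. The plan enrols 45 subjects, excludes women who may be pregnant or lactating, requires contraception, tests at screening, and has a pregnancy-test field on the visit forms.

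Much of this stands. Loose drafting is the likely cause, a careful site might well follow 13.2, and zero pregnancies is plausible. But the narrower reading of 5.8.1 is not written down, and the second paragraph of that section counts against it. Sections 5.3 and 5.9 show that 5.8.1 is out of line with the rest of the plan; they do not correct it. Rarity lowers the expected harm but does not remove the conflict.

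**Conclusion.** The concern holds. As written, 5.8.1 and Sections 13.2 and 13.2.1 give incompatible instructions for a participant who becomes pregnant after taking study drug. This is an internal inconsistency rather than a deliberate design choice.

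Its size can only be bounded. If 5.8.1 is followed literally, the study would seek none of the pregnancy outcomes; if 13.2 is followed, it would seek all of them. Neither bound is a forecast. The documents do not give the number of women of child-bearing potential or an expected number of pregnancies, so no count can be derived.

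The effect is confined to safety follow-up and reporting. The primary endpoint, analysis methods and sample size do not change. The point should be corrected because a stated rule, taken at its word, would forgo safety data that the plan requires elsewhere. It does not rank with defects that affect the trial's inference.

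**What to change.** Reconcile 5.8.1 with 13.2 and 13.2.1 so that the no-further-data rule and the pregnancy follow-up and reporting duty are stated consistently, and add a cross-reference between the sections. Check 5.3 and 5.9 in the same edit, so that each reason for stopping study drug has one stated consequence for later data collection. The content of the clinical rule is for the sponsor-investigator to settle; this review asks only that the passages agree.

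The cost is about one sentence plus the cross-reference, submitted as a protocol amendment to the institutional review board as Section 8.2 requires. No analysis, sample size or visit schedule needs to change on account of this point.

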5.9 Withdrawal from study

A subject may withdraw from the trial at any time at their own request, or they may be withdrawn at any time at the discretion of the investigator for safety, behavioral, or

administrative reasons. If a subject does not return for a scheduled visit, every effort should be made to contact the subject. In any circumstance, every effort should be made to document subject outcome, if possible.

If the subject withdraws consent, no further evaluations should be performed and no attempts should be made to collect additional data; however, they may be questioned regarding their reason for withdrawal and asked to return all unused investigational products.

Patients who withdraw or discontinue from the trial after randomization will not be replaced.

6.1 Recording of data

Case Report Forms (CRFs) for individual patients will be developed by the investigators and served as the source document. Source documents provide evidence for the existence of the patient and substantiate the integrity of the data collected. The study staff will record all medical history, physical examination, safety laboratory assessment and all procedures involved during the study in CRF. Principle investigator will review, sign and date the results. The study staff will communicate with the patients regarding their results and appropriate follow-up and management. It is the sponsor- investigator's responsibility to ensure accuracy, completeness, legibility, and timeliness of the data reported. Data reported in the CRF, that are derived from source documents, should be consistent with the source documents or the discrepancies will be explained by the study staff. Any change or correction to a CRF will be dated, initialled, and explained by the study staff.

6.2 Data collection at enrollment and follow-up

The following data will be collected at enrollment periods (for each study drug period):

1. Vital signs: BP, weight, BMI, HR
2. Blood sample for safety laboratory assessments, glucose control and biomarker for cardiac function (CBCP, CMP including FBG, HbA1c, lipid panel and urine albumin assessment, BNP) (See Table 1)
3. ECGs for heart rate variability studies (LF, HF, LF/HF ratio, SDNN and RMSSD), cardiovascular autonomic reflex tests (E/I ration, Valsalva ratio, 30:15 and orthostatic BP) and RHR
4. Assessment of hypoglycemia by evaluating symptoms and downloading glucometers and glucose log sheets

During follow-up monitoring visits, we will assess hypoglycemia (symptoms, recordings) vital signs, any changes in their medication list, recording of adverse events, serious adverse events and compliance and tolerability of study medications.

At the end of each intervention period, we will repeat the same measures and procedures to obtain primary and secondary endpoints. Those include blood sample for biomarkers, HRV, and CARTs.

We will also evaluate the indices of glucose variability by using Freestyle Libre Pro CGM during each intervention phase in this cohort.

6.2.1 Enrollment procedures

All candidates will be selected from University of Michigan Health System (UMHS), which has a unified electronic medical records system (EPIC) that allows screening in real time for all patients seen at UMHS via best practice alerts. Currently there are ~ 25,000

patients with type 2 diabetes that are being seen in our system. In addition, we have access to the Diabetes Registry, an IRB approved registry of patients with diabetes who provided written consent to have their medical records screened to determine eligibility and to be contacted directly should they be eligible.

Once identified, the candidates will be contacted via phone or email and provided the information regarding the study. Following their review of the study, candidates who express interest in participation will be scheduled for a screening visit (visit 1) in the dedicated research space either within the outpatient clinics of the Division of Metabolism, Endocrinology and Diabetes (MEND) or at the Michigan Clinical Research Unit. (MCRU) (<http://www.michr.umich.edu/services/mcru>) depending on subjects preferences.

Once eligibility is confirmed, candidates will proceed to Visit 2-baseline visit within 4 weeks for randomization and dispensing study medication. Written instructions for use of the medication will be reviewed with and provided to the subject. All participants will be asked to monitor glucose in the morning and before dinner and record in the log book and meter.

